2.1. Primary Objective

The primary objective of the study is:

- To evaluate the safety and tolerability of NTZ 500mg bid after 24 weeks of treatment in patients with NASH induced Stage 2 or Stage 3 fibrosis.

2.2. Secondary Objectives:

The secondary objectives of the study are:

- To determine the effect of daily oral administration of NTZ 500mg bid on de novo collagen synthesis through Fractional Synthesis Rate (FSR) of circulating plasma proteins in patients with NASH-induced Stage 2 or Stage 3 fibrosis.
- To evaluate changes in liver stiffness as measured by FibroScan® and by Magnetic Resonance Elastography (MRE).
- To assess the change from baseline in non-invasive markers of fibrosis: ELF™ test score, PIIINP, Hyaluronic acid, CK18, TIMP-1, YKL-40, Alpha 2 macroglobulin,, ,miRNA, ProC3, ProC6, FGF19, FGF21.
- To assess changes in additional non-invasive tests: fibrosis scores: NAFLD fibrosis score, FIB-4

3. Study Design

3.1. Study Design

This is a phase 2 proof of concept study to evaluate the efficacy and safety of open-label NTZ 500mg bid in a NASH population with NASH induced Stage 2 or 3 fibrosis.

The study will include a screening visit within 6 weeks of randomization (Day 1) followed by a 24-week treatment period consisting of daily, BID, oral administration of NTZ and an end of treatment follow up period of 4 weeks.

Patients will come to the research center and complete the following visits:

- Screening Visit within 6 weeks of Randomization
- Day -14 Deuterated Water Run-In
 - Day-14, Day-11, Day-7 and Day 1: sampling for labelling of Deuterated water during run-in
- Repeat baseline labs for ALT, AST, total bilirubin, ALP, CPK collected at least 4 weeks from initial screening.
- Day 1 Randomization: start of treatment
- Every 4 weeks after randomization until 20 weeks post randomization

- 22 weeks post randomization and Deuterated Water Administration Period:
 - 22 weeks plus 3 days
 - sampling for labelling of Deuterated water on Day 155, 158, 162, and Day 169/24 weeks post randomization: End of Treatment
- 4 Week Post Treatment Follow Up

3.2. Treatment Plan and Regimen

NTZ will be administered in an open label fashion to participating subjects as 500mg bid, for 24 weeks.

4. Subject Population

4.1. Number of Subjects & Subject Selection

Twenty male and female subjects with histologically confirmed NASH and fibrosis stage 2 or 3 will be enrolled in the study at a single site in the United States.

4.2. Inclusion Criteria

Patients must meet all of the following inclusion criteria to be eligible for enrollment in the trial:

1. Males or females aged from 18 to 75 years inclusive the Screening Visit.
2. Must provide signed written informed consent and agree to comply with the study protocol.
3. Females participating in this study must be of non-childbearing potential or using highly efficient contraception for the full duration of the study. Childbearing potential refers to those female subjects who have not had a hysterectomy, bilateral oophorectomy, or medically-documented ovarian failure. Female subjects are considered postmenopausal and not of child-bearing potential if they are >55 years of age, or >50 years of age with >12 months of amenorrhea, or have serum follicle stimulating hormone (FSH) values >40 mIU/ml with >12 months of amenorrhea. Highly efficient contraception is defined as the use of one of the

following methods of birth control in addition to a male partner using a condom (unless surgically sterile) from Screening to 90 days after the last dose of study medication:

- hormone-containing contraceptive
 - intrauterine device
 - cervical cap or diaphragm with spermicidal agent
4. Histological confirmation of steatohepatitis on a diagnostic liver biopsy (biopsy obtained within 6 months prior to Screening or during the Screening Period) with at least 1 in each component of the NAS (steatosis scored 0-3, ballooning degeneration scored 0-2, and lobular inflammation scored 0-3).
 5. Fibrosis stage of 2 or 3, according to the NASH CRN fibrosis staging system on a diagnostic liver biopsy (biopsy obtained within 6 months prior to Screening or during the Screening Period).
 6. Two assessments of ALT, AST, Total bilirubin, ALP, CPK will be collected during screening at least 4 weeks apart. To be eligible the second value cannot be $\geq 2x$ the first value.

4.3. Exclusion Criteria

Patients who meet any of the following criteria will be excluded from entering the study:

1. History of efficient bariatric surgery within 5 years prior to Screening, or planned bariatric surgery in the course of the study.
2. Patients with HbA1c $>10.0\%$. If abnormal at the first Screening Visit, the HbA1c measurement can be repeated. A repeated abnormal HbA1c (HbA1c $>10.0\%$) leads to exclusion.
3. Patients with a history of clinically significant acute cardiac event, or cerebrovascular event, within 6 months prior to Screening such as: stroke, transient ischemic attack, or coronary heart disease (angina pectoris, myocardial infarction, revascularization procedures).
4. Weight loss of more than 10% within 6 months prior to Randomization.
5. Patient with any history or presence of cirrhosis.

6. Current or recent history (within a year of screening) of significant alcohol consumption. For men, significant consumption is typically defined as higher than 30 g pure alcohol per day. For women, it is typically defined as higher than 20 g pure alcohol per day.
7. Current or history of other substance abuse within 1 year prior to screening.
8. Pregnant or lactating females or females planning to become pregnant during the study period.
9. Other well documented causes of chronic liver disease according to standard diagnostic procedures including, but not restricted to:
 - a) Positive hepatitis B surface antigen (HBsAg)
 - b) Positive HCV RNA, (tested for in case of known cured HCV infection, or positive HCV Ab at Screening)
 - c) Suspicion of drug-induced liver disease
 - d) Alcoholic liver disease
 - e) Autoimmune hepatitis
 - f) Wilson's disease
 - g) Primary biliary cirrhosis
 - h) Primary sclerosing cholangitis
 - i) Genetic homozygous hemochromatosis
 - j) Known or suspected HCC
 - k) History or planned liver transplant, or current MELD score >15.
10. Patients who cannot be contacted in case of emergency.
11. Known hypersensitivity to the investigation product or any of its formulation excipients.
12. Patients who are taking warfarin or other highly plasma protein-bound drugs with narrow therapeutic indices.
13. Patients who are currently participating in, plan to participate in, or have participated in an investigational drug trial or medical device trial containing active substance within 30 days or five half-lives, whichever is longer, prior to

Screening. Patients who have screened for, and failed to qualify, for another clinical trial are eligible for screening for the NTZ-218-1, even if the Screening Visit for the NTZ-218-1 study is less than 30 days from the failed study screening visit, provided that the subject received no investigational product within 30 days of 5 half-lives of the investigational product prior to screening for NTZ-218-1.

14. Evidence of any other unstable or, untreated clinically significant immunological, endocrine, hematological, gastrointestinal, neurological, neoplastic, or psychiatric disease.
15. Mental instability or incompetence, such that the validity of informed consent or ability to be compliant with the study is uncertain.
16. History of noncompliance with medical regimens, or patients who are considered to be unreliable.
17. Positive anti-human immunodeficiency virus (HIV) antibody.
18. AST and/or ALT >5 x upper limit of normal (ULN).
19. Total bilirubin >1.3 mg/dL due to altered hepatic function.
20. Direct bilirubin > ULN

Note: Gilbert Disease patients are allowed into the study.

21. INR >1.2 in the absence of anticoagulant therapy.
22. Platelet count <150,000/mm³ in the context of portal hypertension.
23. Significant renal disease, including nephritic syndrome, chronic kidney disease (defined as patients with markers of kidney damage or eGFR of less than 60 ml/min/1.73 m²).

5. Investigational Medicinal Products

Patients will receive 500 mg NTZ (ALINIA®) twice daily for 24 weeks.

5.1. Description

NTZ will be supplied as 500 mg of ALINIA® (nitazoxanide) tablets, for oral use. The tables are round, yellow, film-coated and debossed with ALINIA on one side and 500 on the other side. Each tablet contains 500 mg of nitazoxanide.

For additional information see the Package Insert for ALINIA®.

5.2. Packaging

ALINIA® tablets are packaged in HDPE bottles of 12 tablets. Period boxes will be delivered every 4 weeks, each box containing 6 bottles.

5.3. Labeling

All labels for study drugs meet all applicable requirements of the US Food and Drug Administration (FDA) and the EU annex 13 of Good Manufacturing Practices: Manufacture of Investigational Medicinal Products (February 2010) and /or other local regulations, as applicable.

Distribution of study drug will be performed according to the Good Distribution Practices.

Product boxes for each period will be labeled with the protocol number, Sponsor's name and address, description of contents, storage conditions, expiry date, dosage instructions, and any other applicable items required by national and regional guidelines/regulations. The label will contain the statements "Caution – new drug, limited by Federal Law to investigational use" or other similar/appropriate statements as well as the following instructions "Please return empty packaging and unused products to your doctor at your next visit."

5.4. Storage and Handling

The tablets are to be stored at 20-25°C (68-77°F). Storage conditions are specified on the label.

5.5. Dosage and Administration

Patients will be instructed to take one tablet of 500mg NTZ mg orally, twice a day with water during a meal, approximately 12 hours apart.

The study staff will administer the first dose of the medication at the research center. Patients will self-administer the evening dose on Day 1 and twice a day thereafter, when not attending

a visit at the research center. On scheduled follow up visit days while the patient is being treated with study drug, the patient will be directed to bring back all used and unused study medication containers. Compliance will be checked by the Investigator or designee during those visits and registered in the electronic Case Report Form (eCRF).

If treatment is interrupted, whatever the cause, duration and reason of the interruption will be documented.

5.6. Dose Adjustment

Enrolled subjects who experience treatment emergent adverse events may have their dose adjusted, at the discretion of the Principal Investigator, in accordance with section 6.6.3.

5.7. Prior and Concomitant Medications

In a general manner, patients should be discouraged from starting any new medication without consulting the Investigator unless the new medication is required for emergency purpose. In the same way, any qualitative or quantitative change in concomitant therapy should be avoided, when possible. In the event that it becomes necessary during the study, this should be recorded by the Investigator or designee in the eCRF (including concomitant medications taken within 6 months prior to Screening). This includes drugs used on a chronic as well as on an “as needed” basis.

5.7.1. Non-permitted medication

The following medications are not allowed within the timeframe given:

- Warfarin or other highly plasma protein-bound drugs with narrow therapeutic indices are not permitted from Day 1 until end of treatment

5.7.2. Permitted Medications

Any medications other than those listed above are permitted. However, the dosage of a current medication for a chronic disease should remain unchanged as far as possible in order to reduce the risk of unknown drug-drug interactions.

In the event that additional concomitant therapy becomes necessary during the study, this will be recorded by the Investigator in the eCRF. This includes drugs used on a chronic as well as on

an “as-needed” basis. Patients should be discouraged from starting any new medication without consulting the Investigator unless the new medication is required for emergency purpose.

5.8. Study Drug Accountability

The Investigator will acknowledge receipt for each study treatment on the day of receipt. A drug accountability record will be maintained by the person responsible for dispensing the trial medication to the patient.

All partially used or unused treatments will be inventoried during and at the conclusion of the study.

The Drug Distribution Center will organize the retrieval of all treatments (used or unused) and will proceed to their destruction only after written authorization and review of accountability and distribution records.

6. Study Procedures

The procedures performed at each visit are summarized in the Schedule of Events (Table 1).

A patient may be seen at any time for reasons of safety.

During each visit, safety evaluations will be done, and the patient will be queried in the form of an open question regarding new or continuing events.

6.1. Duration of Study Participation

The estimated duration of the study will be approximately 34 weeks inclusive of the screening period.

6.2. Screening Assessment

Screening Visit

The following screening procedures will be performed for all potential patients at the Screening Visit and prior to Day 1:

- Informed consent witnessed by the Investigator or designated person.

- Medical history & demographics.
- Assessment of inclusion/exclusion criteria
- Complete physical examination.
- Record vital signs
- Record height, weight, BMI
- Check concomitant/prior medication (within 6 months prior to Screening)
- 12-lead ECG
- Liver biopsy. A historical liver biopsy with confirmed NASH and fibrosis is acceptable if performed within 6 months prior to the Screening Visit.
- Adverse Events assessment
- Blood samples will be collected for
 - Biochemistry
 - Hematology
 - Serology (HIV, HBs, HCV). In the event of a positive HCV Ab, HCV RNA can be tested for confirmation. In case of known cured HCV infection, HCV RNA can be tested directly at Screening.
- Repeat baseline labs for ALT, AST, total bilirubin, ALP, CPK collected at least 4 weeks from initial screening.
- Urine samples will be collected for Urinalysis
- Urinary pregnancy test (for women of childbearing potential only [WOCBP]).

If needed, a retesting of any laboratory results may be performed during the screening window to determine the eligibility for the study.

6.3. Day -14 Deuterated Water Run In

Potential Subjects who complete all of the Screening Visit assessments and who continue to be eligible for the study, will return to the research center to complete the Deuterated Water Run In. The visit is to be done on Day -14 \pm 3 days, provided that the subject completes 7 consecutive days of deuterated water administration. The following procedures will be performed at the Day -14 Visit:

- Dispense deuterated water (D₂O). Instruct patient to drink 50ml of deuterated water 3 times per day starting on Day-14 for 7 consecutive days (until day-8).
- Blood sample for baseline labeling by D₂O (kinetic biomarkers) (patients should be instructed to fast the evening prior to the visit to ensure a 10-hour fast)
- Adverse Events assessment
- Record concomitant medication taken

Patients will return at Day-11, Day-7 (\pm 1 day) and Day 1 for blood sampling (labeled D₂O)

6.4. Treatment Period Assessments

6.4.1. Day 1 Visit

The following procedures will be performed at the Day 1 Visit prior to dose administration:

- Review inclusion/exclusion criteria
- Complete physical examination
- Weight, BMI
- Record vital signs
- Record concomitant medication taken
- Adverse Events assessment
- MRE (may be done within \pm 5 days of the visit)
- Fibroscan
- Blood samples will be collected
- Urine samples will be collected for Urinalysis
- Urinary pregnancy test (for women of childbearing potential only [WOCBP]).
- Dispense the study drug as directed
- Review study drug administration instructions with subject
- Administer 500 mg of NTZ with water & food

6.4.2. Week 4 and Week 8 Visit \pm 3 days

The following procedures will be performed at these Visits:

- Record concomitant medication taken
- Adverse Events assessment
- Blood samples will be collected
- Urine samples will be collected for Urinalysis
- Urinary pregnancy test (for women of childbearing potential only [WOCBP]).
- Dispense the study drug as directed
- Review study drug compliance and drug administration instructions with subject
- Reconcile study drug administration using pill counts
- Administer 500 mg of NTZ with water & food

6.4.3. Week 12 Visit \pm 3 days

The following procedures will be performed at the Visit:

- Complete physical examination
- Weight, BMI
- Record vital signs
- Record concomitant medication taken
- Adverse Events assessment
- MRE (may be done within \pm 5 days of the visit)
- Blood samples will be collected
- Urine samples will be collected for Urinalysis
- Urinary pregnancy test (for women of childbearing potential only [WOCBP]).
- Dispense the study drug as directed
- Review study drug compliance and drug administration instructions with subject
- Reconcile study drug administration using pill counts
- Administer 500 mg of NTZ with water and food

6.4.4. Week 16 and Week 20 visits \pm 3 days

The following procedures will be performed at these Visits:

- Record concomitant medication taken
- Adverse Events assessment
- Blood samples will be collected
- Urine samples will be collected for Urinalysis
- Urinary pregnancy test (for women of childbearing potential only [WOCBP]).
- Dispense the study drug as directed
- Review study drug compliance and drug administration instructions with subject
- Reconcile study drug administration using pill counts
- Administer 500 mg of NTZ with water & food

6.4.5. Week 22 Visit \pm 3 days (Day 155)

The following procedures will be performed at the Visit:

- Record concomitant medication taken
- Adverse Events assessment
- Blood samples will be collected for D2O labeling
- Urinary pregnancy test (for women of childbearing potential only [WOCBP])
- Dispense Deuterated water. Instruct patient to drink 50ml of deuterated water 3 times per day starting on Day 155 for 7 consecutive days (until day 162).
- Blood sample for kinetic biomarkers analysis (patients should be instructed to fast the evening prior to the visit to ensure a 10-hour fast)

Patients will return for blood sampling for kinetic biomarker analysis at 22weeks/ \pm 3 days), Day 158, Day 162 (\pm 1 day), and at day 169 (Week 24).

6.4.6. Week 24 Visit \pm 1

The following procedures will be performed at the visit:

- Complete physical examination
- 12-lead ECG
- Record vital signs
- Record weight, BMI

- Record concomitant medication taken
- MRE (may be done within ± 5 days of the visit)
- Fibroscan
- Adverse Events assessment
- Blood samples will be collected
- Urine samples will be collected for Urinalysis
- Urinary pregnancy test (for women of childbearing potential only [WOCBP]).
- Review study drug compliance and drug administration instructions with subject
- Reconcile study drug administration using pill counts

6.5. Follow Up Period

6.5.1. 4-Week Post Treatment Follow up (EOS – End of study visit) ± 3 days

The following procedures will be performed at the visit:

- Complete physical examination
- Weight, BMI
- Record vital signs
- Record concomitant medication taken
- Adverse Events assessment
- Blood samples will be collected Urine samples will be collected for Urinalysis
- Urinary pregnancy test (for women of childbearing potential only [WOCBP]).

6.5.2. Early Termination (ET)

Patients who have discontinued from the study after the first dose of study medication and for any reason will have the following procedures completed:

- Complete physical examination
- Record vital signs
- Weight, BMI
- ECG
- Record concomitant medication taken
- MRE (may be done within ± 5 days of the visit)

- Fibroscan
- Adverse Events assessment
- Blood samples will be collected
- Urine samples will be collected for Urinalysis
- Urinary pregnancy test (for women of childbearing potential only [WOCBP])
- Review study drug compliance with subject
- Reconcile study drug administration using pill counts
- Documentation if Early Termination is due to COVID-19 related AE or concerns.

6.5.3. **Unscheduled Visits**

An unscheduled visit is defined as any visit to the study unit outside of the protocol-evaluation time points where the patient is seen by study unit personnel, e.g., when follow-up assessments are required for safety reasons or when repeat measurements are required out of the screening period (either to confirm a measurement or in case of errors, measuring device failure, etc.).

Unscheduled visits will be needed for patients who may require further follow-up due to safety.

6.6. **Missed or Partially Completed Visits due to COVID-19**

If a subject is unwilling or unable to complete regularly scheduled visit(s) due to COVID-19, the study team will document the following:

- Was the visit partially completed (some procedures completed, while other protocol directed procedures were not completed)? If so:
 - Clinical safety lab tests (hematology, coagulation, pregnancy test, and biochemistry), as required by the visit schedule, must be completed to dispense NTZ to the patient for continued safety monitoring.
- Was any part of the visit performed via a virtual method (e.g. phone, or other technology)? These procedures must be clearly documented as being done “virtually” in the source documentation.
- Description why the visit was partially completed or missed.
- Any COVID-19 related symptoms defined below since the last visit, to include AE onset date, description and resolution date:
 - Fever
 - Cough

- Shortness of breath
- Other symptom as defined by the Centers for Disease Control and Prevention.

6.7. Assessment for Premature Discontinuation from Study

Study medication may be discontinued in the following instances:

- Intercurrent illness that would, in the judgment of the investigator, affect assessments of clinical status to a significant degree. Following resolution of intercurrent illness, the subject may resume study dosing at the discretion of the investigator.
- Subject noncompliance
- Investigator discretion
- Study medication must be discontinued in the following instances:
 - Unacceptable toxicity, or toxicity that, in the judgment of the investigator, compromises the ability to continue study-specific procedures or is considered to not be in the subject's best interest
 - Subject request to discontinue for any reason
 - Pregnancy
 - Discontinuation of the study at the request of a regulatory agency or an institutional review board or independent ethics committee (IRB/IEC)

Pre-specified stopping criteria are defined at the patient level and at the study level. These are described in the following sections 6.6.1., 6.6.2., and 6.6.3. In all cases, when the stopping criteria are met, the Data Safety Monitoring Board will perform causality assessment, and decide whether the study drug/study trial may be continued (See section 6.6.4.).

6.6.1. Pre-specified Patient Discontinuation rules

If a patient experiences a Grade IV Common Terminology Criteria for Adverse Event (CTCAE) or meets liver injury criteria as listed in section 6.6.3., the study drug should be interrupted. After causality assessment by the DSMB, if the AE or lab abnormality is considered unrelated to study drug, and the event has resolved or returned to baseline, then the study drug may be re-

started. If the event reoccurs after restart of study drug, then the study drug will be permanently discontinued.

6.6.2. Pre-specified Trial Discontinuation rules

If one patient experiences a Grade V CTCAE, or 2 patients experience the same Grade IV CTCAE, or 3 patients experience the same Grade III CTCAE, or 4 patients experience the same Grade II CTCAE, the trial will be paused. The DSMB will assess causality of these adverse events; if the events are deemed unrelated to study drug, the trial will continue.

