7.2. Assessment of Adverse Events & Serious Adverse Events

The Investigator will establish whether or not any AE have occurred at each visit from the date of consent. The patient will be questioned in a general manner to determine specific symptoms without offering the patient any suggestion. The investigator or qualified sub-investigator is responsible for assessing AEs and SAEs for causality and severity, and for final review and confirmation of accuracy of event information and assessments.

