7.2.1. Intensity assessment

The intensity of the AE will be graded as follows:

- Mild: Awareness of signs or symptoms, but easily tolerated and are of minor irritant type causing no loss of time from normal activities.

Symptoms do not require therapy or a medical evaluation; signs and symptoms are transient.

- Moderate: Events introduce a low level of inconvenience or concern to the participant and may interfere with daily activities, but are usually improved by simple therapeutic measures; moderate experiences may cause some interference with functioning.
- Severe: Events interrupt the participant's normal daily activities and generally require systemic drug therapy or other treatment; they are usually incapacitating.

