7.3. Reporting

7.3.1. Reporting an adverse event

All AEs regardless of seriousness or relationship to study drug, including those occurring during the Screening Period, are to be recorded on the corresponding page(s) of the eCRF and in the patient’s medical record from the ICF signature until study end for each patient. Whenever possible, symptoms should be grouped as a single syndrome or diagnosis. The Investigator should specify the date of onset, maximal intensity, action taken with respect to study drug, corrective therapy given, outcome, and his/her opinion as to whether there is a reasonable possibility that the AE was caused by the study drug.

Adverse event reporting begins from signature of the patient ICF at the first Screening Visit and ends at study end for each patient.

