8.5.1. Adverse Events

Treatment-emergent adverse events (TEAEs) are defined as AEs that worsen or commence on or after the time of start of first study drug administration. AEs, including SAEs, will be coded using MedDRA. The number and percentage of subjects experiencing TEAE, including TEAEs leading to study drug discontinuation and SAEs, will be summarized for each system organ class (SOC) and Preferred Term. In addition, AEs will be tabulated according to severity, causality, and relation to the study drug.

Individual data listings for AEs will be presented for each subject.

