9.6. Study Files and Retention of Records

The investigator will maintain adequate and accurate records to enable the conduct of the study to be fully documented and the study data to be subsequently verified. These documents should be classified into at least the following two categories: (1) investigator's study master file, and (2) subject clinical source documents. The investigator's study file will contain the protocol/amendments, CRF and query forms, IRB/IEC and governmental approval with correspondence, informed consent, drug records, staff curriculum vitae and authorization forms, and other appropriate documents and correspondence. The required source data should include sequential notes containing at least the following information for each subject:

- Subject identification (name, date of birth, gender);
- Documentation that subject meets eligibility criteria, i.e., history, physical examination, and confirmation of diagnosis (to support inclusion and exclusion criteria);
- Documentation of the reason(s) a consented subject is not enrolled
- Participation in study (including study number);

- Study discussed and date of informed consent;
- Dates of all visits;
- Documentation that protocol specific procedures were performed;
- Results of efficacy parameters, as required by the protocol;
- Start and end date (including dose regimen) of IMP, including dates of dispensing and return;
- Record of all adverse events and other safety parameters (start and end date, and including causality and severity);
- Concomitant medication (including start and end date, dose if relevant; dose changes);
- Date of study completion and reason for early discontinuation, if it occurs.

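### The stopping rules count CTCAE grades that the protocol's adverse event scale does not record, and the dose-adjustment section has no grade limit or stated precedence against the Grade IV rule

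*Protocol*

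**What the plan says.** **Rules that need a CTCAE grade.** Protocol 6.6.1 interrupts study drug in a patient with a Grade IV CTCAE event or liver injury. Restart is allowed only if the DSMB judges the event unrelated and it has cleared or gone back to its baseline level. Section 6.6.2 pauses the trial for one patient with Grade V or two with the same Grade IV, and continues: "3 patients experience the same Grade III CTCAE, or 4 patients experience the same Grade II CTCAE, the trial will be paused". No CTCAE version is given anywhere.

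**What is recorded.** Section 7.2.1 opens with "The intensity of the AE will be graded as follows" and lists three levels: mild, moderate and severe. Its top level covers events that interrupt "normal daily activities and generally require systemic drug therapy or other treatment; they are usually incapacitating". The other places that describe AE content name intensity or severity and no grade:

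- 7.2: the investigator is "responsible for assessing AEs and SAEs for causality and severity".
- 7.3.1: "The Investigator should specify the date of onset, maximal intensity, action taken with respect to study drug, corrective therapy given, outcome".
- 8.5.1: "AEs will be tabulated according to severity, causality, and relation to the study drug".
- 9.6, source data: "Record of all adverse events and other safety parameters (start and end date, and including causality and severity".

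SAP 3.5.1 summarises AEs by maximum severity. It states a MedDRA version but no severity scale.

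**Dose adjustment.** Section 6.6.3 applies to treatment-emergent AEs at the principal investigator's discretion, with no grade limit. After a three-day hold, a patient whose symptoms have cleared stops NTZ for good. A patient whose symptoms persist goes back on 500 mg once daily.

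**The concern.** Two rules meant to protect patients do not connect cleanly to the rest of the protocol.

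First, the pause rule counts patients by CTCAE grade, and the AE record described in the protocol has no grade. Safety and tolerability is the primary objective of this single-arm study. If the grade is not recorded, neither the DSMB nor a later reader can confirm from the listed AE data that a pause was due, or that one was correctly not called.

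Second, 6.6.1 and 6.6.3 give different instructions for a patient whose event has not cleared. If 6.6.3 were applied to a Grade IV event, it would direct a restart that 6.6.1 withholds. The absence of a Grade IV field makes it harder to see from the record which section applies.

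**Working it through.** The documents give no operating characteristics for the stopping rules, and the sample size of 20 rests on clinical assessment (Protocol 8.7). There is no figure of the plan's own to reproduce. The check is a comparison of texts, with one calculation for scale.

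**Step 1. Can the listed AE data supply the grade?**

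| The rule needs | What the documents offer |
|---|---|
| Grade V | No intensity level. Death is an SAE criterion (7.1.3) and fatal is an outcome (7.2.3), which could stand in. |
| Grade IV | No level above severe. The life-threatening SAE criterion (7.1.3) could stand in for part of it. |
| Grade III | Severe is the nearest level, shared with the rest of Grade IV. |
| Grade II | Moderate is the natural candidate, but this is not stated. |
| Liver injury | Numeric ALT and bilirubin limits in 6.6.4. Identifiable without a grade. |

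The documents make none of these links themselves. The gap that matters lies in the clause "2 patients experience the same Grade IV CTCAE, or 3 patients experience the same Grade III CTCAE": two different counts, with one recorded level (severe) for both once life-threatening SAEs are set aside.

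**Step 2. How much could the choice of trigger matter?**

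The counts of 2, 3 and 4 patients are 2/20 = 10%, 3/20 = 15% and 4/20 = 20% of the sample. Let X be the number of patients with one specific event, binomial with n = 20 and rate p. The rates below are assumptions, because the documents give none for any single Grade III or IV event.

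- P(X ≥ 2) = 1 − (1−p)^20 − 20p(1−p)^19
- P(X ≥ 3) = P(X ≥ 2) − 190p²(1−p)^18

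At p = 0.05: P(X ≥ 2) = 1 − 0.3585 − 0.3774 = 0.264 and P(X ≥ 3) = 0.264 − 0.189 = 0.075.

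| Assumed p | Pause at 2 patients | Pause at 3 patients |
|---|---|---|
| 2% | 6% | 1% |
| 5% | 26% | 8% |
| 10% | 61% | 32% |
| 15% | 82% | 60% |

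The error can go either way. A Grade IV event counted at three patients moves the chance from the middle column to the right one. A Grade III event counted at two patients moves it from right to middle. Protocol 1.2.2 describes gastrointestinal AEs as generally mild, so the low rates may be nearer.

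**Step 3. Sections 6.6.1 and 6.6.3 side by side.**

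Take a non-liver Grade IV TEAE and suppose the 6.6.3 hold is used.

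| State after the hold | 6.6.1 | 6.6.3 as written | Result |
|---|---|---|---|
| Resolved, unrelated | May restart | Permanent stop | Compatible, since 6.6.1 only permits restart |
| Resolved, related | Stay off | Permanent stop | Agree |
| Unresolved, unrelated | Stay off | Restart once daily | Conflict |
| Unresolved, related | Stay off | Restart once daily | Conflict |

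The sections conflict in 2 of 4 cases, both unresolved. The branches of 6.6.3 look inverted. If they were swapped, the two unresolved conflicts would vanish and one would appear in the resolved and related case, where 6.6.3 would restart and 6.6.1 would not.

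**Step 4. Does the protocol say which section prevails?**

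Section 6.7 gives the DSMB the decision whenever stopping criteria are met. It names 6.6.1, 6.6.2 and 6.6.3 as the sections holding those criteria, and sends the reader to 6.6.4 for the DSMB, which is described in 6.6.5. Section 6.6.1 points to 6.6.3 for liver criteria that are in 6.6.4. Section 6.6.5 also cites 6.6.3. Section 6.6.4 gives the set that makes sense: 6.6.1, 6.6.2 and itself. The pattern looks like pointers left behind when the sections were numbered. No sentence states precedence between 6.6.1 and 6.6.3.

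**The case against.** The strongest reply is that a sensible reader already knows what to do. Section 6.6.1 is the specific Grade IV rule, 6.7 puts the continuation decision with the DSMB and requires drug to stop for unacceptable toxicity, and 6.6.3 is discretionary, with gastrointestinal, kidney and musculoskeletal events as its examples. This largely stands. A reader might infer that the protocol permits re-dosing of an unresolved Grade IV event. The documents do not support that, because it follows only if 6.6.3 is read in isolation. What remains is a collision between two texts with no stated order.

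A reader might also infer that quarterly DSMB meetings are too slow for a three-day hold. That does not follow either. The quarterly review is routine, while 6.6.1, 6.6.4 and 6.7 describe review triggered by events, and under 6.6.1 a slow answer leaves the patient off drug.

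On grading, the eCRF and DSMB charter are not among the documents and may carry a CTCAE grade, and nothing confines the DSMB to the 7.2.1 scale. Moderate may also serve adequately for the Grade II trigger. Both points are fair. They narrow the problem to Grade III against Grade IV and to what the protocol and SAP themselves specify. Finally, a trigger brings a pause for causality review, not a stop, and every rate in the calculation is assumed.

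**Conclusion.** The point holds in a limited form and should be fixed.

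The patient and trial rules act on CTCAE grades that the AE record in the protocol and SAP does not contain. Apart from deaths, life-threatening SAEs and liver events, a severe event cannot be assigned to the two-patient or the three-patient trigger, so the listed AE data cannot confirm whether a pause was due. This assumes that no unseen document supplies the grade. The pause probabilities show only that the choice of trigger could matter. They do not estimate what happens in this trial.

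Separately, 6.6.3 has no grade limit, and as written it contradicts 6.6.1 for unresolved Grade IV events. Section 6.6.1 probably governs. The apparent inversion in 6.6.3 reaches further, because it affects every patient put on a hold, at any grade.

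**What to change.** 1. In 7.2.1 and on the eCRF AE page, record the CTCAE grade for every AE, with the version stated. Use that grade for the 6.6.1 and 6.6.2 triggers and for the SAP 3.5.1 severity tables. If the eCRF or charter already carries it, one sentence in 7.2.1 and one in SAP 3.5.1 are enough.
2. Limit 6.6.3 to non-liver TEAEs of Grade III or lower. State that 6.6.1, 6.6.4 and the DSMB decision govern Grade IV and liver events. Confirm or correct the resolved and unresolved branches. If they are intended, as a test of whether the event clears off drug, say so.
3. As a clerical edit in the same amendment, correct the pointers: 6.6.1 to 6.6.4 for liver criteria; 6.7 to 6.6.1, 6.6.2 and 6.6.4 for stopping criteria and to 6.6.5 for the DSMB; 6.6.5 to 6.6.1, 6.6.2 and 6.6.4.

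The cost is one eCRF field and amendment wording, with no extra patients, visits or procedures.
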